Aim 2. Measure tobacco use patterns across IQOS flavor availability conditions to assess clinical lab result validity. During 7-day naturalistic evaluation outside of the clinical lab, participants will respond to daily Ecological Momentary Assessment (EMA) prompts by reporting OB and IQOS use.  $H_{2A}$ : Those in the IQOS-menthol condition will have a larger percentage reduction in average daily cigarettes consumed per day (Tues-Thurs) from the baseline to the intervention week, than those in the IQOS-tobacco condition.  $H_{2B}$ : IQOS use/day higher during the intervention week (Tues-Thurs) will be higher in the IQOS-menthol condition compared to the IQOS-tobacco condition.  $H_{2C}$ : Those with access to IQOS-menthol will replace a greater percentage of their total tobacco product consumption (cigarettes + IQOS) with IQOS products during the intervention week (Tues-Thurs) than will those with access to IQOS-tobacco.

Hypothesis  $H_{1A}$ ,  $H_{1D}$ , and  $H_{2A}$  constitute primary outcomes. All other hypothesis represent secondary outcomes.

#### Primary Study Endpoints:

*Aim 1:* For sub-hypothesis A, the outcome is the baseline-adjusted plasma nicotine concentration following a 10-puff directed bout with the participant's randomly assigned IQOS product on Friday of the intervention week. For sub-hypothesis B, the outcome is the average duration of the puffs taken during the 10-puff directed puffing bout with the participant's randomly assigned IQOS product on Friday of the intervention week. For sub-hypothesis C, the outcome will be the degree of cigarette craving suppression from before to after the directed puffing bout with the participant's randomly assigned IQOS product on Friday of the intervention week. Sub-hypothesis D will consider differences in IQOS' cross-price-elasticity obtained during the ETM performed on Friday of the intervention week between those with access to IQOS-M and IQOS-T and those with

access to IQOS-T only. Sub-hypothesis E will compare the baseline-adjusted plasma menthol-glucuronide following a 10-puff directed bout between IQOS-M and IQOS-T groups on Friday of the intervention week.

*Aim 2:* The primary EMA outcome (H2A) is the percentage reduction in average daily consumption of cigarettes (Tues-Thurs) from the baseline to the intervention week (e.g., 10 cigs/day in baseline week to 2 cigs/day in intervention week = 80% reduction). The outcome for H2B is the average daily number of IQOS HeatSticks used on Tues-Thurs of the intervention week. The outcome for H2C is the percentage of average daily consumption of tobacco products (cigarettes + IQOS) consumed during the intervention week (Tues-Thurs) that are IQOS HeatSticks.

- 2. Overview of Design. Once enrolled, eligible participants will complete a two-arm, parallel group, 14-day clinical lab study (Aim 1) of IQOS that includes naturalistic assessment (Aim 2; see Table 1). First, participants will complete a 7-day positive-control, own-brand (OB) menthol cigarette baseline. Then, for the second 7-day period, participants will be randomized (1:1 allocation; stratified by gender (Male vs Female) and race (African American/Black vs non-African American/Black) to receive either IQOS-M or IQOS-T and instructed to attempt to use their assigned product as a complete cigarette substitute. The baseline and intervention weeks will feature clinical lab sessions (Monday and Friday) and daily naturalistic use assessments.
- **3.** Participants. A total of 50 community volunteers who currently use menthol cigarettes will be randomized in this study (25 per condition; randomization will stratify across gender (Male vs Female) and race (African American/Black vs non-African American/Black).

### **Inclusion Criteria**

- Healthy adults (aged 21 and older)
- Smoke at least 5 cigarettes per day for at least 1 year (i.e., established, daily smokers)
- Regular cigarette brand is flavored to taste like menthol or mint
- Exhaled Carbon Monoxide (CO) reading of > 5 PPM at in-person screening, as well as a 'positive' cotinine cassette result, to verify smoking status/nicotine use at the in-person screening.
- Report no intention to quit smoking in the next 3 months
- Participants must be willing to provide informed consent and abstain from nicotine/tobacco for ≥8 hours prior to each lab session.
- Participants must have access to a computer/smartphone and be willing to receive and respond to daily surveys
- Able to read and write in English

### **Exclusion Criteria**

- Daily use of any tobacco products other than cigarettes
- Self-reported history of unstable or significant medical conditions in the past 12 months. These include: uncontrolled high blood pressure (via self-

report or observed at screening; BP must be less than 160/100 at screening), heart-related conditions (e.g., recent heart attack/stroke, coronary heart disease), severe immune system disorders (e.g., HIV/AIDS, multiple sclerosis), respiratory disorders (e.g., COPD, asthma), kidney diseases, liver diseases (e.g., cirrhosis), or seizures.

- Individuals with other self-reported current, diagnosed medical conditions (e.g., diabetes, thyroid disease, lyme disease) will be considered for exclusion after consultation with the PI and medical monitor. Participants with any medical condition/medication that may affect participant safety, study outcomes, or biomarker data will be excluded based on these consultations.
- Individuals with current, diagnosed, psychiatric conditions that are uncontrolled will be excluded. A controlled psychiatric illness is defined as one where the individual is taking medication and/or receiving other treatment (e.g., psychotherapy). In addition, individuals who have been to the ER and/or been hospitalized for a psychiatric condition in the past year will be excluded.
- Cannabis use >15 days, alcohol use >25 days, and any other illicit drug use (e.g. cocaine, opioids, etc.) in the past 30 days.
- Women will be excluded if they test positive for pregnancy (by urinalysis) or self-report breastfeeding.

These inclusion and exclusion criteria are consistent with those employed by [name] recently awarded clinical trial (R01DA050996 [HM20022060]) and previous studies conducted at the VCU Center for the Study of Tobacco Products, including 2 F31 awards (F31DA047018 [HM20015258] and F31DA054780 [HM20018418]).

- 4. Recruitment and Enrollment. Participants will be recruited by institutional review board-approved advertisements and by word of mouth. The BHRL and CSTP Tobacco User Registries are available to aid recruitment efforts. Interested individuals will use the BHRL or CSTP website to complete a screening survey online (i.e., "brief pre-screener") or call the BHRL or CSTP to complete the same survey via phone to determine initial eligibility.
- 5. Consent process. Following documentation of initial eligibility, participants will be contacted to confirm their initial interest in the study and invited to an inperson screening session where consent will be obtained. Prior to the in-person session, we will provide all participants with an unsigned copy of the consent form for them to review via email. Researchers will be available in-person and via email/phone to answer any questions participants may have about the study during the consent process. See SmartForm for more detail on the consenting process.

[figure not shown]
# 6. Study Procedures.

[figure not shown]
The study is divided into 3 phases: Screening/Enrollment, Baseline Week (use OB menthol cigarettes), and Intervention Week (use randomly-assigned) IQOS product. In the Screening/Enrollment phase, participants will complete the CSTP/BHRL registry to assess initial eligibility for this study and those deemed potentially eligible will be invited to an in-person screening session at the CSTP. At this session, informed consent will be obtained, eligibility confirmed, and baseline/demographic information collected. At the end of the in-person screening session, all eligible and consenting participants will be given an opportunity to take 4 test puffs of the IQOS product (flavor: Tobacco). During the baseline and intervention weeks, participants will complete clinical lab sessions (see "Aim 1" below) and naturalistic use assessments (see "Aim 2" below). Please note, at the start of each in-person activity, participants will answer 4 questions to screen for COVID-19 as with the CSTP's other ongoing projects (all answers must be "no" in order to continue). Randomization will occur at the beginning of the first clinical lab session (Monday, Baseline week) to allow for the proper ETM to be displayed during all subsequent sessions.

	Pre- screen	Screen	Mon	Tues -Thurs	Fri	Sat-Sun	Mon	Tues-Thurs	Fri	Sat-Sun
Week	NA	0	1	1	1	1	2	2	2	2
Phase	Screening/Enrollment Baseline Week (Own-Bra			nd Menthol Cigarettes)		Intervention week (IQOS-menthol or IQOS-tobacco)				
Main Activity	Online Survey	In-person screening + Test Puffs	Lab Visit 1 + Randomization	Natural Use (EMA)	Lab Visit 2	Natural Use (EMA)	Lab Visit 3 + IQOS Distribution	Natural Use (EMA)	Lab Visit 4	Natural Use (EMA)
Time	10 min	60 min	120 min	3 min/day	120 min	3 min/day	120 min	3 min/day	120 min	3 min/day
Relevant Measures	Baseline Demographics, Health, and Tobacco Use		Aim 1	Aim 2	Aim 1	Aim 2	Aim 1	Aim 2	Aim 1	Aim 2

Aim 1: During the course of the clinical lab study set forth in Aim 1, participants will complete directed puffing bouts (10-puffs, 30 second interpuff interval) with either OB (baseline week) or their randomly-assigned IQOS product (intervention week). The interpuff interval is defined as the time between the start of 1 puff and the beginning of the next (Hiler et al., 2017). This procedure requires physiological monitoring of heart rate and blood pressure (sessions will be stopped if blood pressure ever exceeds 180/120) and venipuncture and/or catheter placement will be completed by [name], RN. One blood sample (7 mLs) will taken immediately before and immediately after a standard, controlled 10-puff directed puffing bout (total of 14 mL per session). A total of 56 mL of blood will be sampled for the entire study; this amount of blood sampling will occur at 4 sessions over a 12 day period and is less than a standard blood donation that is provided in a single sitting (473 mL). Outcome measures include changes in plasma nicotine and menthol concentration from pre- to post- puffing bout and subjective effects, including cigarette craving suppression as well as the direct effects of OB and IQOS. Following this procedure, participants will then complete an Experimental Tobacco Marketplace (ETM). In the ETM, participants will be asked to make purchasing decisions across an array of tobacco/nicotine products, including IQOS and OB, as their OB become increasingly expensive (prices will be presented in random order at each session [i.e., the order of pricetrials will be randomly determined for each session, but within a session each participant will face the same order of price-trials]). The minimum task time for the ETM will be set to 20 minutes (i.e., if a participant finishes all questions in the ETM before 20 minutes, they'll cannot progress to the next portion of the session until 20 minutes has elapsed). The primary outcome of interest is the cross-price elasticity of demand for IQOS as a function of OB price. Each session will begin by obtaining an exhaled Carbon Monoxide breath sample, as will be done in the in-person screening session, and asking participants whether they've abstained from using tobacco or nicotine products in the last 8 hours. Moreover, on the 2 Friday sessions, participants will complete a short "timeline follow back" assessment to report on their usage of cigarettes, IQOS, and other tobacco products during the preceding 3-days (Tues-Thurs). A timeline of session structure is provided below.

Though every effort will be made to have participants complete the study on the prescribed timeline (in-person screening, 2 baseline week visits [Mon, Fri], 2 intervention week visits [Mon, Fri]), we recognize that things outside the participant's or the researcher's control could impact completion of the study on this schedule. Thus, to handle the event in which a participant misses a session, we have devised the following plan. If an in-person screening session is missed, that session will be rescheduled at the participant's convenience. If the participant misses 1 of the baseline week visits, we will NOT reschedule the missed session – the single baseline visit that was completed will be used as the control comparison in statistical analyses. If both baseline visits are completed, the Friday results will be used as the control comparison. If a participant misses their Monday intervention week visit, we will reschedule for the next Monday on which the participant is available and commence the week as normal from that point. If a participant misses their Friday intervention week visit, we will reschedule for the next business day on which the participant is available. Friday intervention week sessions will not be rescheduled such that the "naturalistic" use period is any less than 3 full days (i.e., the rescheduled session will occur the following week).

Aim 2: In addition to the clinical lab sessions, participants will report usage of OB and their randomly assigned IQOS product daily by responding to ecological

momentary assessment (EMA) prompts (text or email) sent each morning of the 2-week study window. Surveys will be sent at 8 AM each day; if a participant has not responded by noon a reminder text/email will also be sent. Outcomes are primarily concerned with responses to EMA prompts on Tuesday, Wednesday, and Thursday of each week – but prompts will be sent daily to encourage habit formation and compliance. Participants will use their OB during the baseline week.

On Monday of the intervention week, at the conclusion of the clinical lab session, participants will be given an IQOS 2.4 Tobacco Heating System, HeatSticks in their randomly-assigned flavor (Fresh Menthol or Regular Tobacco), and brief instructions for use (including a handout with accompanying video). Participants will be provided with the same number of HeatSticks as cigarettes they reported consuming during the baseline week, plus 20% to account for potential product loss or increases in use. Participants will be instructed "We are providing you with an a heated tobacco product known as IQOS in [condition-specific flavors] over the next week to be used as a substitute or complete replacement for your own brand cigarettes. We want to understand how you use these specific heated tobacco products as well as your own brand cigarettes when they are the only products available to you. Therefore, please refrain from using all other nicotine/tobacco products and other heated tobacco product flavors for the duration of the study. If you use anything else, it is important that you tell us what you used. Additionally, please return all of the IQOS product and any unused HeatSticks at your lab visit on Friday."

Study Period	Pre- screen	In-person Screening	Clinical Lab Sessions	Daily Surveys
Study Days	NA	0	1, 5, 8, and 12	1-14
Demographics	Х	Х		
COVID-19 Screening Questionnaire		Х	Х	
Heart Rate and Blood Pressure Monitoring		Х	Х	
Urine pregnancy and cotinine tests		Х		
Exhaled Carbon Monoxide		Х	Х	
Tobacco Use History	Х	Х		
Drug & Alcohol Use		Х		
Health and Medical History	Х	Х		
Reasons for flavored tobacco use		Х		
Contact information		Х		
Cigarette Dependence (PROMIS 4A and PSNDI)		Х		
Stage of Change / Quit Confidence		Х		
Test Puffs (4) of IQOS-Tobacco		Х		
Adverse Events			Х	
3-day Timeline Follow Back			X (Days 5 and 12 only)	

7. **Measures.** Participants will complete the measures in the timeline shown below.

Product Evaluation Questionnaire	X	
Subjective Effects Questionnaire	X	
Plasma Nicotine and Menthol	v	
Collection		
Puff Topography	X	
Experimental Tobacco Marketplace	X	
Ecological Momentary Assessment		Х

Baseline/Screening and Cigarette/Tobacco Measures: We will assess contact information, demographics (e.g., age, gender, race, ethnicity, income, occupation), tobacco use history, other drug/alcohol use, and health and medical history including health/psychiatric conditions (e.g., Medical History Form used in P50DA036105-Project 3), reasons for flavored tobacco use (CASEL Flavors Working Group, 2021), cigarette dependence (PROMIS 4A; Shadel et al. 2014, Penn State Nicotine Dependence Index [PSNDI], Foulds et al., 2015), stages of change/quitting confidence using standardized items from PhenX and national surveys (e.g., PATH; BRFSS; TUS-CPS), and items/measures adapted for menthol cigarettes. Additionally, those that attend the inperson screening but are deemed ineligible because their blood pressure exceeds the limits set in the inclusion/exclusion criteria will be given a letter explaining their test result and directed to resources that can help them in the management of hypertension.

- 8. Compensation. Participants will be compensated for their time: \$25 for inperson screening, \$2 for each complete EMA assessment (14 total), \$50 for each of two Monday sessions, and \$100 for each of two Friday sessions. Total possible compensation for this study amounts to \$353. We'll also reimburse participants up to \$12/session for parking, if needed.
- 9. Statistical Analysis Methods and Sample Size/Power. 50 participants will be needed to obtain power ≥0.80 to detect a difference between subjects on the plasma nicotine outcome, with alpha<0.05 (G\*power 3.1.9.7). The power analysis was based on previous studies (Ns ~30) where effect sizes of the main effect of condition were large for ETM outcomes (d>1.16), medium for plasma nicotine (d>0.76), and large for reduction in average daily number of cigarettes (d>2.66).

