Exploratory analyses compared the observed *cross-price intensity* of IQOS (i.e., demand for IQOS at the lowest price of OB menthol cigarettes [\$0.12/cigarette]) across the IQOS-M and IQOS-T groups using Mann-Whitney U tests. CPE estimates for all other alternative products were compared across experimental groups using Mann-Whitney U tests (individual-level analyses) and a linear combination of parameters (group-level analyses). Wilcoxon Signed Rank tests compared ETM outcomes (within-group) across sessions 2 (OB, Fri) and 4 (IQOS, Fri) as well as across sessions 3 (IQOS, Mon) and 4 (IQOS, Fri) to gauge if exposure to IQOS in the clinical laboratory or at home influenced purchasing decisions in the ETM.

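### Sections 2 and 6 disagree on when participants are randomised; if it is day 1, as Section 6 says, the H2A baseline is collected after allocation

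*Combined protocol and SAP*

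**What the plan says.** Two sections give the order of events differently.

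- Section 2, Overview of Design: "First, participants will complete a 7-day positive-control, own-brand (OB) menthol cigarette baseline", followed by "Then, for the second 7-day period, participants will be randomized (1:1 allocation".
- Section 6, Study Procedures: "Randomization will occur at the beginning of the first clinical lab session (Monday, Baseline week) to allow for the proper ETM to be displayed". The schedule table in the same section agrees, labelling the Monday of week 1 "Lab Visit 1 + Randomization".

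The ETM comes after the puffing bout within a lab session: "Following this procedure, participants will then complete an Experimental Tobacco Marketplace (ETM". Section 7 marks it for the lab sessions, which fall on days 1, 5, 8 and 12. According to the ETM part of the Aim 1 Analyses, the IQOS-M group can buy both HeatStick flavours and the IQOS-T group only the tobacco flavour.

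On the own-brand comparator, Section 6 says "If both baseline visits are completed, the Friday results will be used as the control comparison". If one baseline visit is missed it is not rescheduled, and the other visit serves. The ETM comparison over time is within group: "Wilcoxon Signed Rank tests compared ETM outcomes (within-group) across sessions 2 (OB, Fri) and 4 (IQOS, Fri".

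The Aim 2 Analyses define H2A as the percentage fall in daily cigarettes from Tuesday-Thursday of week 1 to Tuesday-Thursday of week 2. It is self-reported and compared between arms by a Mann-Whitney test with no adjustment. Section 1 lists H1A, H1D and H2A as primary.

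**The concern.** A baseline used to compute a between-arm outcome should be fixed before allocation, so that nothing about the arm can influence it. Under Section 6 the H2A denominator is collected on days 2 to 4, after allocation on day 1. The measure is self-reported, and the plan does not say who is kept unaware of the allocation. If the arm-specific ETM is shown at session 1, participants will also have seen an array that differs by arm before they report those counts.

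The second consequence concerns losses. Anyone who leaves during week 1 has been randomised but has received no IQOS, and can contribute nothing to the session-4 or week-2 outcomes. Section 10 allows the investigator to withdraw people for not following instructions. With allocation already made, such withdrawals are post-randomisation exclusions that could depend on the arm.

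**Working it through.** **Timeline under Section 6**

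| Event | Study day | Relative to allocation |
|---|---|---|
| Screening, tobacco use history | 0 or before | before |
| Randomisation, start of Lab Visit 1 | 1 | – |
| First ETM, later in Lab Visit 1 | 1 | after |
| H2A baseline counts (Tues-Thurs) | 2–4 | after |
| Session 2: timeline follow-back, own-brand bout, ETM | 5 | after |
| IQOS handed out, flavour disclosed | 8 | after |
| Session 4: H1A and H1D outcomes | 12 | after |

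The only information on cigarette use collected before allocation is the screening history, which H2A does not use. Neither planned H2A sensitivity analysis helps. The timeline follow-back baseline is taken on day 5, and the multiple imputation fills gaps in the same post-allocation counts.

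**Which primary tests are exposed.** H1A compares nicotine boost (post-puff minus pre-puff within one session) between arms at session 4. H1D compares cross-price elasticity between arms at session 4. Neither uses a week-1 value in the between-arm test. The comparisons of IQOS with own brand are within group. Only H2A carries a week-1 measurement into a primary between-arm test.

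**Does the stated reason need day 1?** The planned ETM comparisons use sessions 2, 3 and 4. Session 1 enters only as a fallback when the Friday baseline visit is missed. IQOS is first needed at session 3, and the strata (gender and race) are known from screening.

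**A gap in the visit rules.** Section 6 ties randomisation to the Monday baseline visit but also lets that visit be missed without rescheduling. No rule says when such a participant is randomised. If it were done on Friday, that person's H2A baseline would precede allocation while the others' would follow it.

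**Sensitivity of H2A to its denominator.** With b the week-1 mean and w the week-2 mean, H2A = 100 × (b − w)/b. The plan's own example reproduces: 100 × (10 − 2)/10 = 80%. The documents give no figure for a reporting shift, so the values of b other than 10, and w = 5, are assumptions:

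| Reported b | w = 2 | w = 5 |
|---|---|---|
| 8 | 75.0% | 37.5% |
| 9 | 77.8% | 44.4% |
| 10 | 80.0% | 50.0% |
| 11 | 81.8% | 54.5% |

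A shift of 1 cigarette/day from 10, in one arm only and with week 2 unchanged, moves H2A by 1.8 to 2.2 points (w = 2) or 4.5 to 5.6 points (w = 5). A shift from 10 to 8 moves it by 5 or 12.5 points. A shift common to both arms would not favour either arm.

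**Week-1 losses.** No rate is given. At an assumed 5% to 20%, 50 × 0.05 = 2.5 to 50 × 0.20 = 10 of the 50 randomised would never receive IQOS.

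**The case against.** The strongest case is that most of the mechanism is inferred.

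- Section 2 can be read loosely as naming the week for which a product is assigned, while Section 6 states the timing explicitly, twice, with a reason. The loose reading is possible, but the plain order of Section 2's sentences is the reverse of Section 6, so the wording still has to be reconciled.
- Section 6 speaks of displaying the proper ETM at all subsequent sessions, which could exclude session 1. Randomising at the start of session 1 for this purpose makes inclusion the natural reading, not a certain one. If the display began on day 5, the days 2–4 counts would precede the cue but still follow allocation.
- Both arms smoke their own brand in week 1, and all eligible participants are offered the same tobacco-flavour test puffs. It is not obvious why seeing menthol HeatSticks in a purchase task would alter reported cigarettes. Flavour is known in week 2 whenever randomisation occurs, so later randomisation leaves that route of reporting bias untouched. This stands, and it is why neither size nor direction can be claimed.
- People lost in week 1 supply no week-2 data under either design. That also stands. What changes is whether they are lost before or after randomisation.

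A reader might infer that staff and participants knew the arm during week 1. The documents do not say so: they are silent on masking in that week, and the only stated disclosure of flavour is when IQOS is handed out on day 8. A reader might also infer that the nicotine and elasticity outcomes rest on a compromised baseline. They do not, because their between-arm tests use session 4 alone.

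**Conclusion.** The point holds as an inconsistency between Sections 2 and 6, and as an avoidable risk of bias to H2A alone among the primary between-arm tests. That the H2A baseline and week-1 losses follow allocation is a direct consequence of Section 6. That the arm-specific ETM is seen at session 1 is probable. That anyone's knowledge of the arm alters week-1 reporting is a possibility the plan does not exclude, and no bias has been demonstrated. The 2 to 6 points rest on an assumed one-arm shift of 1 cigarette/day around a baseline of 10 and week-2 smoking of 2 to 5 a day; the true size and direction are unknown. H1A and H1D are affected only if week-1 losses differ by arm. The change is worth making because the risk falls on a primary outcome and the stated reason for day-1 randomisation can be met almost entirely without it.

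**What to change.** Randomise at session 2 (Friday, week 1), after the timeline follow-back and own-brand bout and just before that session's ETM. If session 2 is missed, randomise at the start of session 3. At session 1 use one common array or no ETM. If Thursday's cigarettes are reported through Friday's prompt, require that response before allocation. Make Sections 2 and 6 agree. The planned between-group look at own-brand self-reported effects at session 2 then becomes a check of balance before allocation.

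Costs:

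- Participants who miss session 2 would have no arm-specific baseline ETM. This affects only the exploratory within-group comparison. A common array at session 1 must either include or omit menthol HeatSticks, so it will differ from one arm's later arrays.
- Section 3 must say whether 50 is the number entering week 1 or the number randomised. If 50 enter, the number analysed is unchanged, but at the assumed 5% to 20% loss only about 47.5 to 40 would be randomised. Randomising 50 would need 50/0.95 = 52.6 to 50/0.80 = 62.5, that is 53 to 63 entrants.

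The analysis sections are written in the past tense, so conduct may be over. In that case, or if day-1 randomisation is kept, correct Section 2, state who knew the allocation during week 1, and report week-1 losses by arm. Add an H2A sensitivity analysis that uses cigarettes/day from the pre-randomisation screening history as the baseline. This assumes the screening form records a usable daily count; the requirement of at least 5 cigarettes a day suggests it does. Because it is a different instrument from the daily prompts, it tests whether the conclusion is robust but does not measure the bias.
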